3.2. Interim Analysis

A formal interim analysis is planned in Protocol Amendment 2. Patient enrollment was paused while the conspicuity score criteria was developed. A total of 21 patients were randomized and treated at the time of enrollment pause. Since the study total sample size of approximately 116 patients to be enrolled will remain unchanged for the protocol amendment, and that the 21 subjects enrolled prior to 5-point conspicuity score is developed will be excluded from the final efficacy analysis (see Section 3.3), the timing of this planned interim analysis will be based on the enrollment of the remaining approximately 95 subjects. That is, this formal interim analysis is to be conducted when approximately 50% of the remaining patients are randomized and treated (approximately 47-48 patients). The objective of this interim analysis is to confirm the observed treatment effect size on the conspicuity score from the test dataset. The interim analysis will only analyze the conspicuity score provided by the central reviewers.

Since randomization to the IC dose level will not be unblinded during the interim analysis, the overall IC treatment effect will be analyzed using the proportional odds model; the model will include the main effect of treatment (IC vs Saline) and ureter (left vs right) and control for the repeated measures within a subject. This model is identical to the reduced model (Model 2) in the primary analysis of the primary endpoint described in **Section 5.1**.

Conditional Power (CP) will be calculated based on estimated odds ratio and corresponding standard error in log scale from the interim analysis data based on equation from Lan and Wittes

(1988) as summarized by professor Gary Kock in 2003 at Drug Information Association (DIA) 10th Annual Biostatistics Workshop in Japan, August 29, 2003 in Tokyo, Japan¹.

The prediction of the conditional power for a statistically significant result from the final analysis (at the two-sided 0.05 level) given the observed difference between treatments at a formal interim analysis can be based on the estimated treatment effect (equation 2); 2-sided 95% confidence intervals for the CP will also be calculated.

2. Estimated conditional power if the observed treatment difference at the interim analysis applies to the remainder of the study

$$\text{ProbNorm} \left\{ \left[\sqrt{\frac{(1-P)}{P}} + \sqrt{\frac{P}{(1-P)}} \right] Z - \frac{Z_\alpha}{\sqrt{1-P}} \right\}$$

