where $Z = (\hat{T} / \text{SE})$

3. 100(1- γ) confidence interval for conditional power on the basis of \hat{T} and SE

$$\text{ProbNorm} \left\{ \sqrt{\frac{(1-P)}{P}} \times (Z \pm Z_\gamma) + \sqrt{\frac{P}{(1-P)}} \times Z - \frac{Z_\alpha}{\sqrt{1-P}} \right\}$$

Where T_{hat} = estimate of treatment effect at interim and SE = standard error of the treatment effect. In this study, T_{hat} will be the estimate of odds ratio of treatment and SE will be the standard error of the estimate, both are in the log scale. P =proportion of study completed (=0.5), alpha (α)=0.05/2, gamma (γ)=0.05

Following Mehta et al (2011, page 6)² adaptive approach the interim analysis results will be classified into three zones based on the estimated CP and decision to be made in each zone is specified as follows.

¹ Page 8 “Statistical Considerations for the Conduct and Reporting of Interim Analyses”. (GGK 8/11/2003)

² Adaptive increase in sample size when interim results are promising: A practical guide with examples. Cyrus R. Mehta and Stuart J. Pocock. Statist. Med. 2011, 30 3267--3284

Table 3: Interim Analysis Conditional Power and Decision Principle

Conditional Power	Decision	Rationale
CP <0.20	Stop the study because the evidence for unfavorable efficacy is sufficiently convincing that no additional efficacy data is necessary.	An unfavorable zone: the conditional power (CP) is fairly low, suggesting that the final result is not likely to achieve significance, hence, the study has fairly low probability to reject the null hypothesis. This zone is defined to be CP < 40%
0.2 <=CP <0.4	No sample size re-estimate because the evidence for unfavorable efficacy. Complete the study per current protocol.	
0.4 <=CP <=0.8	Re-estimate sample size, study continues to complete the enrollment per re-estimated sample size	A Promising zone: the conditional power is in between 40% to 80%, suggesting that the interim analysis result is promising, but the study has to have an increased sample size to have at least 80% power to reject the null hypothesis
CP > 0.8	No sample size re-estimate. Complete the study per current protocol.	A favorable zone: the conditional power is fairly high, suggesting that the interim result is as good or better than the expectation, the study has fairly high probability to reject the null hypothesis as is. This zone is defined to be CP > 80%.

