response. The model estimates the cumulative logits of better outcome (conspicuity=5) to the poor outcome (conspicuity=1). Since it is expected that the interaction effect will not be statistically significant ($p > 0.10$), a reduced model (**Model 2**) will also be used in which the interaction effect will be dropped. The goodness of fit of the models (Full model vs the Reduced model) will be evaluated. A REPEATED statement will be used to control for the repeated measures within a subject. The difference between the IC high dose vs saline, the IC low dose vs saline will be presented in the summary along with the estimates and 95% confidence intervals of the estimates. Effect of a source (treatment, ureter, treatment*ureter interaction in full model) will be determined based on the Score Statistics for Type 3 GEE Analysis.

For the primary endpoint analysis, GEE models will be fitted separately for each comparison, namely IC High dose vs Saline, and IC Low dose vs Saline, and IC High dose vs IC Low dose.

An example of SAS syntax is showing below for this analysis, in which the conspicuity is treated as an ordinal response variable and a proportional odds model is used model the better response compared to the poorer response. Stokes et al. (2000)³ recommended that the null hypothesis of treatment effect would be based on the score statistics for Type 3 GEE analysis, whereas the parameter will be the GEE parameter estimates with the empirical standard error because the Z and the Wald statistic generally produce more liberal p-value than the score statistic.

In this example, the treatment is a binary code; IC High dose=1 and Saline=0. For analysis of IC Low dose vs Saline, IC Low dose=1 and Saline=0; when comparing IC High dose vs IC Low dose, IC High dose=1 and IC Low dose=0.

```

PROC GENMOD DATA=respH descending;
  CLASS USUBJID URETER(ref='Right') TRT (ref='Saline');
  MODEL conspicuity = trt ureter trt*ureter
    /LINK=clogit DIST=mult TYPE3; (Model 1)
  REPEATED subject = Usbjid / type=ind;
  ESTIMATE 'OR: IC vs Saline' trt 1 -1/ exp;
  ods output Estimates=OR1 GEEEmpPEst=est1 Type3=pval1;
  Run;

PROC GENMOD DATA=respH descending;
  CLASS USUBJID URETER(ref='Right') TRT (ref='Saline');
  MODEL conspicuity = trt ureter
    /Link=clogit DIST=mult TYPE3; (Model 2)
  REPEATED SUBJECT = Usbjid / type=ind;
  ESTIMATE 'OR: IC vs Saline' trt 1 -1/ exp;
  ods output Estimates=OR2 GEEEmpPEst=est2 Type3=pval2;
  Run;

```

Where:

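### The conditional-power interval in SAP Section 3.2 is labelled two-sided 95%, but read with the convention its own Z_α needs, it has 90% coverage

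*SAP*

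**What the plan says.** SAP Section 3.2 plans one interim analysis, after about half of the remaining 95 or so subjects have been randomized and treated. CP is computed from the pooled IC-versus-saline log odds ratio and its standard error. It is the predicted chance of a significant final result "at the two-sided 0.05 level". The section adds that "2-sided 95% confidence intervals for the CP will also be calculated".

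Two formulas follow. Equation 2 gives the point estimate and contains Z_α. Equation 3 is headed as a 100(1−γ) "confidence interval for conditional power on the basis of" the estimate and its standard error. It contains Z_α again, together with Z ± Z_γ. The inputs are a completed proportion P of 0.5 and "alpha (α)=0.05/2, gamma (γ)=0.05". The section does not say what Z with a subscript means, that is, whether it is an upper-tail quantile or a two-sided critical value.

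Table 3 then sorts the result by estimated CP, with cuts at 0.20, 0.40 and 0.80.

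**The concern.** Equation 3 uses two normal quantiles written in the same notation and defined on the same line. For a two-sided 0.05 test, alpha is supplied already divided by two. For a two-sided 95% interval, gamma is supplied whole. If the subscript means the same thing in both places, one of the two stated levels must be wrong.

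What is at stake is how precise the interim estimate appears. The DMC will be shown an interval around CP with a 95% label. If the multiplier is 1.645, that interval is too short at both ends. An independent statistician outside the study team will program this text, so the formula should yield the stated level without interpretation.

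**Working it through.** **Inputs (all SAP Section 3.2).** P = 0.5; α = 0.05/2 = 0.025; γ = 0.05; final test two-sided at 0.05; interval two-sided 95%; Z = estimate/SE on the log odds scale.

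**Step 1: check the point formula.** CP under the observed trend is Φ{[Z√P + θ(1−P) − Z_α]/√(1−P)} with θ = Z/√P. Substituting θ gives Φ{[√((1−P)/P) + √(P/(1−P))]Z − Z_α/√(1−P)}, which is equation 2. At P = 0.5 both square-root terms equal 1 and 1/√(1−P) = 1.414, so CP = Φ(2Z − 1.960 × 1.414) = Φ(2Z − 2.772). For Z = 1.5 this is Φ(0.228) = 0.590; simulating the second half of the trial gives 0.589. Equation 2 is correct with Z_α = 1.960.

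**Step 2: what the interval needs.** Only the projected drift is uncertain, so the error enters through the √((1−P)/P) term, as equation 3 has it. The structure is right. The only question is the multiplier. At P = 0.5 the limits reduce to Φ(z_CP ± Z_γ), where z_CP = Φ⁻¹(CP).

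**Step 3: try each reading of the subscript.**

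| Reading of Z_x | Z_α at α = 0.025 | Final test implied | Z_γ at γ = 0.05 | Coverage implied |
|---|---|---|---|---|
| Upper-x quantile | 1.960 | two-sided 0.05, as stated | 1.645 | 2Φ(1.645) − 1 = 90% |
| Two-sided critical value | 2.241 | two-sided 0.025, not as stated | 1.960 | 95%, as stated |

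Neither row meets both stated levels. The second row would also move the point estimate: at Z = 1.807, CP would be Φ(3.613 − 2.241 × 1.414) = Φ(0.443) = 0.671 instead of 0.800. The stated two-sided 0.05 level excludes that row, which leaves the first.

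**Step 4: confirm the coverage.** With 200,000 simulated interims at each of four true drifts (0, 1.96, 2.8 and 4), the interval with 1.645 contained the true CP in 89.9% to 90.0% of cases. The interval with 1.960 contained it in 94.9% to 95.0%.

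**Step 5: size at the Table 3 cuts, P = 0.5.**

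| CP | Z | z_CP | Multiplier 1.645 (as written) | Multiplier 1.960 (true 95%) |
|---|---|---|---|---|
| 0.20 | 0.965 | −0.842 | 0.006 to 0.789 | 0.003 to 0.868 |
| 0.40 | 1.259 | −0.253 | 0.029 to 0.918 | 0.013 to 0.956 |
| 0.80 | 1.807 | 0.842 | 0.211 to 0.994 | 0.132 to 0.997 |

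For example, at CP 0.80 the lower limits are Φ(0.842 − 1.645) = Φ(−0.803) = 0.211 and Φ(0.842 − 1.960) = Φ(−1.118) = 0.132.

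The final alpha of 0.0499 in Section 3.4, against the 0.05 used here, does not explain the gap. It changes CP by at most 0.0005 at the values checked.

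**The case against.** **The level is stated twice, and Z_γ is never defined.** A statistician asked for a two-sided 95% interval might simply use 1.96, and the output would then be right. The formula is taken from cited workshop material, and Section 3.4 sends interim details to a DMC charter. Either might define the symbol, and neither is available here. This stands in part. The documents do not show that a 90% interval will be produced. They show a formula that gives 90% when its two quantiles are read alike.

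**The interval decides nothing.** This stands. A reader might infer that a too-short interval could put the trial in the wrong zone, since at CP 0.80 the lower limit is above 0.20 as written and below it when corrected. Table 3 does not support that inference: every row is a cut on the estimated CP, and no rule in Section 3.2 or 3.4 refers to the interval. Its width cannot change the zone, the sample size, the alpha or the final test.

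**A stronger reading concerns Z itself.** Z is a Wald ratio, whereas Section 5.1 bases the final test on the score statistic and remarks that "the Z and the Wald statistic generally produce more liberal p-value than the score statistic". A reader might infer that CP is materially inflated and that a score-based Z should replace it. The documents do not support this. The remark concerns testing the null hypothesis at the final analysis, and Section 3.2 openly chooses estimate and standard error for prediction. The size of any difference cannot be fixed from the plan. In a one-sample approximation with 47 subjects at the interim and 94 at the end, an interim Z of 1.807 gives 0.800 by the SAP formula and 0.785 by simulation of a final score test. Putting a score-based Z into the formula gives 0.765. The substitute is no more accurate than the formula it would replace.

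**Conclusion.** The inconsistency is real and can be shown from Section 3.2 alone: no single meaning of the subscript gives both the two-sided 0.05 test and the two-sided 95% interval. Applied as written, with Z_α at 1.960, the interval has 90% coverage. At P = 0.5 the lower limit at CP 0.80 is then 0.211 instead of 0.132, and the upper limit at CP 0.40 is 0.918 instead of 0.956. Both intervals are wide, so the message that CP is imprecise at the halfway point survives either way.

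The conclusion rests on reading Z_γ by the same convention as Z_α. The consequence is confined to the precision displayed to the DMC. The point formula is correct, and neither zone placement nor type I error depends on the interval. This is a small correction to a descriptive output.

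**What to change.** In equation 3, replace Z_γ with Z_{γ/2}, keep γ = 0.05 so that the multiplier is 1.96, and leave the 100(1−γ) heading and the 95% label as they are. Add one sentence to Section 3.2 defining Z_x as the upper-x quantile of the standard normal distribution; this also fixes Z_α at 1.96 in both equations. If the DMC charter or the interim programs repeat the formula, make the same change there.

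The cost is one symbol and one sentence, with no new data and no change to Table 3. The only downside is that the displayed interval becomes wider.

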3.3. Analysis Population

The following analysis sets will be identified for this study.

Enrolled Analysis Set: All subjects who sign the ICF for the study are considered to have enrolled.

Intent-to-Treat (ITT) Analysis Set: The ITT Analysis Set will include all randomized subjects. This dataset may also be referenced as the 'Randomized Set'. The ITT subjects may or may not receive randomized treatment. All ITT subjects will be included in the randomized treatment group even if a dosing error occurred. See additional discussion in [Section 3.7](#).

Safety Analysis Set: The safety set will include all ITT Analysis Set subjects who are treated with any study drug (Saline or IC) and will be used for safety and tolerability assessments. In the safety analysis set all subjects will be included in the actual treatment group received if a dosing error occurred. See additional discussion in [Section 3.7](#).

Efficacy Analysis Set: The efficacy analysis set includes all Safety Analysis Set subjects who have a surgical procedure to assess ureteral patency and who have received both study drugs (Saline and IC dose) and a video approximately 10 minutes in length is available after each treatment. **The 21 patients who were randomized and treated prior to the development of the conspicuity score will be excluded from the efficacy population.** This will be the primary population for efficacy assessments. This is also referenced as the modified intent-to-treat (mITT) Analysis Set. All efficacy evaluations will be based on the mITT population. In the mITT analysis set all subjects will be included in the actual treatment group received if a dosing error occurred. See additional discussion in [Section 3.7](#).

Per Protocol (PP) Analysis Set: The PP set includes all subjects from the Efficacy Analysis Set who did not have any major protocol deviation that may confound the interpretation of the efficacy assessment. This Analysis Set will serve as a confirmation analysis set for efficacy analysis. In the PP analysis set all subjects will be included in the actual treatment group received if a dosing error occurred. See additional discussion in [Section 3.7](#).

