3.8.3.1. Missing Data Imputation Rules for TTV

In order to calculate TTV, the injection start time and time when blue color is adequate visualized in the ureter jet flow must be present. Although the clinical team will make the best effort to eliminate missing or partial time, mistakes could occur. The following rules will be implemented should a subject had missing or partial injection time or time when blue color in the ureter jet flow is adequately visualized.

1. When the injection start time is missing or partial

- 1) If injection start time is missing but the completion time is present, the missing start time will be set to be the same as the injection completion, and vice versa.
- 2) If the hour and minutes are non-missing but the seconds are missing for injection start time, the first second (01) will be assigned to the injection time.
- 3) Otherwise the median elapsed time (defined as time between surgery start time and injection start time) in the study across all subjects who did not have missing data will be used to impute the missing time. That is, the missing injection start time will be set as (Surgery start time + median elapsed time).

The rules will be implemented based on this order.

2. When event occurred but the time is missing or partial

A subject is considered to have had this event when the conspicuity score is 4 or higher per central reader score for this ureter. When a subject has this event but the time when the event occurred is missing, the following rules will be applied.

- 1) If the time is partial (i.e., only the seconds are missing), the first second (01) will be assigned.
- 2) If the time is missing, the subject will not be censored for this endpoint. The missing time, however, will be assigned to 10 minutes after the injection start time.
- 3) This event will be considered as an important protocol deviation. The subject will be excluded from the efficacy PP analysis set. A sensitivity analysis may be performed for the TTV endpoint based on the efficacy PP analysis set.

If a subject had issue(s) with a ureter initially this subject will be censored for this analysis regardless if the issue(s) is or is not fixed during the procedure.

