4.4. Protocol Deviations

All protocol deviations will be identified and will be classified as either an 'Important Protocol Deviation' or 'Protocol Deviation'.

Important Protocol Deviation: An Important Protocol Deviation is a protocol deviation that may significantly impact the completeness, accuracy, and/or reliability of the study data or that may significantly affect a subject's rights, safety, or well-being. Examples may include:

- Failure to meet all entry criteria;
- Non-compliant with study drug treatment regimen;
- Did not receive randomized treatment due to dosing error;
- Use of prohibited concomitant medications;

Protocol Deviation: Any alteration/modification, divergence or departure from the IRB-approved protocol. A protocol deviation is an unanticipated or unintentional divergence or departure from the expected conduct of an approved study that is not consistent with the current research protocol, or consent document.

All protocol deviations will be tabulated by protocol type, protocol deviation category for each treatment group and study overall (**Table 14.1.4**) based on the safety analysis set.

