³ Stokes ME, David CS, Koch GG (2000). Categorical Data Analysis using the SAS System 2nd Edition (page 485).

1. Dataset respH include subjects from IC High dose only.
2. The ‘descending’ option indicates that the ordered values are listed in descending order.
3. Conspicuity score (1, 2, 3, 4, or 5)
4. ‘TRT’ is Treatment (coded to IC or Saline)
5. ‘URETER’ is coded to ‘Left’ or ‘Right’
6. ‘USUBJID’ is the unique Subject Identification
7. REPEATED statement controls the intra-subject correlation due to repeated measures. In this example, independent correlation matrix is used.
8. Three output datasets:
 - a. OR=estimated odds ratio (IC /Saline)
 - b. EST= Analysis of GEE Parameter Estimates based on Empirical Standard Error Estimates
 - c. PVAL= P-value for each effect in the model per Score Statistics For Type 3 GEE Analysis

The analysis summary table (**Table 14.2.1.1**) will include distribution of conspicuity score in each treatment group by ureter (left vs right and overall), p-value based on score statistics for Type 3 GEE analysis, odds ratio estimates and standard error, and 95% confidence intervals for the odds ratio. Three treatment group comparisons will be provided, namely difference between IC High dose vs Saline, IC Low dose vs Saline and IC High dose vs IC Low dose (an exploratory analysis).

The summary table will display the nominal p-values from each comparison (High dose vs Saline, Low dose vs Saline, and High dose vs Low dose). However, the statistical significance of the normal nominal p-value between the IC High dose vs Saline and between the IC Low dose vs Saline will follow the rule defined in [Section 3.4](#) in order to control for family-wide type I error for the primary endpoint.

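### The High-versus-Low comparison has no as-randomized version, and the SAP does not settle whether subjects given the wrong dose belong in the per-protocol set

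*SAP*

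**What the plan says.** Only the IC dose is randomized. SAP Section 3.7 describes two randomization groups, High and Low, and every subject receives saline first. The SAP handles a dosing error as follows.

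- ITT set (Section 3.3): "All ITT subjects will be included in the randomized treatment group even if a dosing error occurred".
- Efficacy set, also called mITT (Section 3.3): "In the mITT analysis set all subjects will be included in the actual treatment group received if a dosing error occurred". The same section adds: "All efficacy evaluations will be based on the mITT population".
- PP set (Section 3.3): efficacy-set subjects "who did not have any major protocol deviation that may confound the interpretation of the efficacy assessment". It continues: "In the PP analysis set all subjects will be included in the actual treatment group received if a dosing error occurred".
- Section 3.7 applies dose received to efficacy and safety, and makes a dosing error an important protocol deviation. Section 4.4 gives as an example of that class: "Did not receive randomized treatment due to dosing error".
- Section 3.8.3.1, on a missing TTV event time, states: "This event will be considered as an important protocol deviation. The subject will be excluded from the efficacy PP analysis set".

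High versus Low is labelled exploratory in Sections 2 and 5.1. Section 3.4 limits Type I error control to the two IC-versus-saline hypotheses for conspicuity.

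**The concern.** Randomization protects High versus Low and nothing else in this trial. The saline contrasts are within subject and in a fixed order. If the dose given differs from the dose assigned for a reason linked to the patient or the case, grouping by dose received lets that reason into the dose comparison. A set named modified intent-to-treat would normally guard against this, but here only the ITT set keeps the assigned groups, and no efficacy analysis uses it.

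The PP problem is one of definition. Under one reading, wrong-dose subjects stay in PP under the dose they received. Under the other, an important deviation bearing on efficacy removes them. Two programmers could build two different PP sets. The choice carries into Sensitivity Analysis 2 of the primary endpoint (Section 5.1.1), which is restricted to PP subjects and is described as free of all potential confounding. It also carries into the count that decides whether the other PP tables are produced (Section 5).

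**Working it through.** **1. Which set keeps the assigned dose, and where it is used**

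| Set | Group after a dosing error | Efficacy use (Sections 3.3, 5, 5.1.1, 8.1) |
|---|---|---|
| ITT | as randomized | none |
| mITT | as received | all efficacy tables |
| PP | as received | Sensitivity Analysis 2; repeat tables if the 10% rule is met |

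High versus Low is estimated for conspicuity (5.1), satisfaction (5.2), responder difference (5.3), TTV hazard ratio (5.4) and concordance (5.5.3). Section 3.7 presents satisfaction by randomization group. It uses the same label for laboratory tests and ECG, whose analysis set goes by dose received, so this is not a clear as-randomized exception.

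**2. Sample available.** 116 − 21 = 95, matching the approximately 95 in Section 3.2. Section 3.7 expects the saline group to be twice the size of each dose group, which implies equal allocation: 95/2 = 47.5 per dose.

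**3. What as-randomized analysis would cost.** The documents give no dosing-error rate, so a range is assumed. With k swapped doses spread evenly over the arms, e = k/95 and the share of a true difference retained is 1 − 2e. Take 47 per arm, two-sided 0.05, and an effect giving 80% power without errors: d = √(2/47) × (1.960 + 0.842) = 0.578 SD.

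| k | retained | power |
|---|---|---|
| 0 | 100% | 80% |
| 1 | 97.9% | 78% |
| 2 | 95.8% | 77% |
| 5 | 89.5% | 71% |
| 10 | 78.9% | 60% |

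**4. What as-received analysis could cost.** Assume no dose effect, 47 assigned High and 48 assigned Low. Suppose k Low subjects are given High and differ by b SD from the rest. Then n_H = 47 + k and n_L = 48 − k, bias = kb/n_H + kb/n_L, SE = √(1/n_H + 1/n_L), and the error rate is Φ(−1.96 + bias/SE) + Φ(−1.96 − bias/SE). For k = 2 and b = 1: bias = 2/49 + 2/46 = 0.084, SE = 0.205, error rate 7.0%.

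| k | bias, b = 0.5 to 1 SD | nominal 5% becomes |
|---|---|---|
| 1 | 0.02–0.04 SD | 5.1–5.5% |
| 2 | 0.04–0.08 SD | 5.5–7.0% |
| 5 | 0.11–0.21 SD | 8.1–17.8% |

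**5. Extreme bound.** A simulation took 48 High and 47 Low with two correlated ordinal IC scores per subject, no dose effect, and 400 trials per setting. Regrouping the 1, 2 or 3 Low subjects with the poorest IC scores as High moved the mean High/Low odds ratio from 1.0 to 0.89, 0.79 or 0.71. Regrouping at random left it between 0.98 and 1.01.

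**6. PP texts side by side.** Section 4.4 has two classes, important deviations and other protocol deviations. Section 3.3 excludes on a third word, major, which the SAP neither defines nor links to those classes. Sections 3.7 and 4.4 put a dosing error in the important class. Section 3.3 nevertheless says which group such a subject joins within PP, which presupposes that the subject is still there.

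**7. PP trigger.** 10% of 95 is 9.5, so 10 exclusions are needed, and a wrong-dose subject kept in PP does not count toward them. Section 5 says more than 10% and Section 8.1 says at least 10%. At 95 both give 10; at 90 they give 10 and 9.

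**The case against.** The strongest reply is that nothing confirmatory is touched. High versus Low is exploratory and carries no alpha. The dose-received rule is prespecified, and Section 3.7 requires dosing errors to be documented in the report and the database. The surgeon is blinded to dose and the central readers to treatment and dose, and the dose is given before the IC score exists. All of this stands. It makes outcome-related errors unlikely but does not exclude them: the study is open-label, and the documents do not say that the person giving the injection is blinded.

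A second reply is that changing the grouping for one comparison makes Table 14.2.1.1 mix two meanings of High and Low. That is a real cost, and a footnote has to deal with it. It is also true that as-randomized grouping within mITT does not fully restore randomization, because mITT already requires both injections and two usable videos.

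On PP, the regrouping sentence is repeated almost word for word across the safety, mITT and PP definitions, and it may only label whoever remains. That makes the text ambiguous rather than proof that wrong-dose subjects are kept. The main protocol body is not among the documents, so the statement that major is undefined applies to the SAP only.

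A reader might infer from Section 3.8.3.1 that every important deviation removes a subject from PP. It does not say so; it is one specific exclusion for a missing TTV time. Using the whole important class would also be wrong, since Section 4.4 includes deviations affecting rights or safety that have no bearing on efficacy.

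**Conclusion.** The point holds as a minor one, in two parts. The only randomized comparison has no as-randomized analysis, and membership of PP is unclear for subjects given the wrong dose.

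There is no effect if no dosing errors occur, and no bias if they are random. With one or two errors, all in one direction and in subjects who differ by 0.5 to 1 SD, an exploratory 5% test runs at about 5.1% to 7.0%. Five such errors would give 8.1% to 17.8%. The number of errors and the size of the difference are assumptions, because the documents give neither.

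Three stronger readings are not supported.

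- The primary tests are not harmed. Regrouping moves a subject's saline and IC scores together from one dose dataset to the other, so the within-subject pairing stays intact.
- Odds ratios of 0.89 to 0.71 are not an expected effect. They select errors by a score not yet observed when the dose is given.
- PP is not useless as a confirmation set. A subject given the other study dose and grouped by it is still a valid saline–IC pair. What fails is the clarity of the definition, and with it the description of Sensitivity Analysis 2 as free of confounding.

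**What to change.** 1. In Sections 3.3 and 3.7, state that High-versus-Low efficacy comparisons (conspicuity, responder difference, TTV hazard ratio) use the randomized dose within mITT, with dose received as a sensitivity analysis. Keep dose received for the IC-versus-saline contrasts and for safety. Footnote each affected table with the grouping used for each comparison. Say which grouping applies to satisfaction.
2. In Section 3.3, define PP exclusions as those important deviations of Section 4.4 that may confound the efficacy assessment, keeping that existing limit. State that dosing errors are among them, and delete the sentence that regroups such subjects within PP. Use one form of the 10% rule in Sections 5 and 8.1.

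The cost is SAP wording, one more grouping variable, a few sensitivity rows and a footnote, best settled before database lock. The statistical price is slight dilution of the exploratory dose contrast if errors occur: about 2% of a true difference for one swap and 4% for two.
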